3.3 Study Procedures and Flowchart

Study subjects or subjects' parent/legal representative will be informed by study staff of the possibility for enrollment in the PMS study while attending a visit at the participating clinic or hospital, for the purpose of vaccination with MenACWY-CRM according to the local routine clinical care.

Informed consent must be obtained from the subject, or where applicable, the subject's parent(s) or legally acceptable representative(s) prior to the performance of any study related procedures.

At the visit, for each subject, data will be collected on the respective source document and then recorded on the appropriate section of the CRF.

Visit 1 - Day 1

- Written informed consent from the subject or subject's parents/legal representative, will be obtained.
- It will be checked whether subject conforms to inclusion and exclusion criteria (see section 4.0).
- Medical history will be collected and recorded on the Medical History CRF.
- A physical exam/assessment, including height, weight and body temperature (preferably axillary) will be performed and results recorded before vaccination.
- Demographic data will be collected and recorded.
- The study vaccine will be administered intramuscularly in the deltoid, preferably of the non-dominant arm. If the investigator determines that the subject's health on the day of vaccination temporarily precludes vaccination, according to the indication reported in the vaccine leaflet, the visit may be rescheduled.
- The subject will be observed closely for at least 30 minutes in the clinic after vaccination, with appropriate medical treatment readily available in case of a rare anaphylactic reaction following the administration of vaccines. Any local or systemic reaction observed within 30 minutes post vaccination will be recorded in the Adverse Event CRF.
- All subjects, or, where applicable, the subject's parents/legal representative, will be dispensed a Diary Card with instructions on how to complete it:
 - Days 1-7: record all local (erythema, induration, pain) and systemic (chills, nausea, malaise, myalgia, arthralgia, headache, rash, fever) reactions, all other AEs and SAEs, and all medications used to treat them;
 - Days 8-29: record all medically attended AEs and SAEs and all medications used to treat them.

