2.4 Study Method

In order to obtain information on Regulatory PMS data after-market launch, or delegate will create the Regulatory PMS contract with the relevant clinics/hospitals and the physician in charge of the survey shall implement this Regulatory PMS in subjects that receive MenACWY-CRM in the relevant hospital/clinic since the contract date until the number of contracted survey cases, without omission, is reached.

Overview of Study Design

This is a multicenter post marketing surveillance study to monitor the safety of MenACWY-CRM administered according to the prescribing information to 3,960 healthy subjects from 2 months to 55 years of age in Korea.

Subjects will be enrolled at the time of their visit to a participating clinic or hospital for vaccination with MenACWY-CRM according to the routine clinical care.

	CONFIDENTIAL :	Last Update Date
	THIS DOCUMENT AND INFORMATION CONTAINED HEREIN IS PROPRIETARY TO COMPANY AND IS NOT TO BE DISCLOSED WITHOUT THE WRITTEN PERMISSION OF COMPANY.	20-APR-2018
STATISTICAL ANALYSIS PLAN(V6.0)		

At Visit 1 (Day 1), after obtaining consent from the subjects or subjects’ parents/legal representative (and Assent Form, if required by the relevant IRB), the vaccination will be administered. Subjects will remain under observation for at least 30 minutes in the clinic after study immunization.

The subjects or subject’s parent/legal representative will be then instructed to complete the Diary Card daily, reporting local and systemic adverse events and all other AEs occurring within 7 days following immunizations, and medically attended AEs or SAEs occurring up to Day 29 within the surveillance period after each study vaccination.

Subjects will also be instructed to return the completed diaries to the study site at Day 29 as follows:

- During a visit at the study center or
- Using the provided pre-addressed stamped envelope (PASE).

At the investigator discretion, the subject or subject’s parent/legal representative will be reminded of the date of the study termination by a phone call at Day 29. If any clarification is required after Diary Card retrieval the site staff will follow up by phone, and any additional finding will be recorded on the subject’s medical record.

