In case the Diary Card is not retrieved within 10 days after Day 29, subject or subject’s parent/legal representative will be contacted by phone to assess the occurrence of adverse events, determine the subject’s clinical status and complete study termination. All information will be recorded by the site staff on the subject’s medical record and collected in the appropriate section of the CRF.

All SAEs will be monitored until resolution and/or the cause is identified. If a SAE remains unresolved at study termination, a clinical assessment will be made by the investigator and the GSK regional physician to determine whether continued follow up of the SAE is needed.

Table 3.1-1: Safety Assessment Table

Medical History: All significant past diagnoses including all allergies, major surgeries requiring inpatient hospitalization, other significant injuries or hospitalizations, any conditions requiring prescription or chronic medication (i.e., >2 weeks in duration), or other significant medical conditions based on the investigator’s judgment.
	
From birth, collected at clinic visit Day 1

---	--

	CONFIDENTIAL :	Last Update Date
	THIS DOCUMENT AND INFORMATION CONTAINED HEREIN IS PROPRIETARY TO COMPANY AND IS NOT TO BE DISCLOSED WITHOUT THE WRITTEN PERMISSION OF COMPANY.	20-APR-2018
STATISTICAL ANALYSIS PLAN(V6.0)		

Immediate reactions: Subjects will be assessed for immediate hypersensitivity reactions.
	For at least 30 minutes after vaccination

Solicited local adverse events: < 6 years : injection site erythema, injection site induration, injection site tenderness ≥ 6 years : injection site erythema, injection site induration, injection site pain
	Days 1-7 after vaccination

Solicited systemic adverse events: < 6 years : change in eating habits, sleepiness, irritability, rash, vomiting, diarrhea, fever ≥ 6 years : chills, nausea, malaise, generalized myalgia, generalized arthralgia, headache, rash, fever
	Days 1-7 after vaccination
All unsolicited AEs will be collected	Days 1-7 after vaccination

Medically attended Adverse Events: Events that require a physician's visit or an emergency room visit (events that are managed by telephone or means other than a face-to-face evaluation by a clinician do not qualify as medically attended AEs).
	From Day 1 to study termination (Day 29/early termination)

Serious AEs: All SAEs will be collected.
	From Day 1 to study termination (Day 29/early termination)

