4.1 Safety Endpoints

Safety will be assessed after administration of study vaccine in terms of the number and percentage of subjects with:

- Local and systemic solicited adverse events reported from study Day 1 (day of vaccination) through study Day 7 post-vaccination;
- Unsolicited AEs reported from study Day 1 (day of vaccination) through study Day 7 post-vaccination;
- Medically attended AEs reported from study Day 1 to study termination (Day 29/early termination);
- SAEs reported from study Day 1 to study termination (Day 29/early termination).

5. Assessment Criteria

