6.2.3 Analysis of Unsolicited AE

All unsolicited AEs and MAAE recorded in the CRF will be mapped to preferred terms using the most recent MedDRA dictionary and classified by System organ class (SOC) and Preferred Terms (PT). Under the classification standard of MedDRA terms, and all AEs excluding the AEs whose causal relation with the study medication is ‘Not Related’ shall be treated as AEs whose causal relation cannot be excluded {hereafter “Adverse Drug Reaction(ADR)”}.

- ① The frequency and percentage of unsolicited AE (Day 1-7) and MAAE (Day 1-29) according to the expected, serious, severity, frequency, action taken, outcome, relationship to MenACWY-CRM regarding occurred AE will be calculated.
- ② The frequency of unsolicited AEs (Day 1-7) and MAAE (Day 1-29) will be classified into the preferred terms according to the expected, serious, severity, frequency, action taken, outcome, relationship to MenACWY-CRM.
- ③ The number of subjects and percentage of SAE/Serious ADR (SADR), unexpected AE/ADR,

	CONFIDENTIAL :	Last Update Date
	THIS DOCUMENT AND INFORMATION CONTAINED HEREIN IS PROPRIETARY TO COMPANY AND IS NOT TO BE DISCLOSED WITHOUT THE WRITTEN PERMISSION OF COMPANY.	20-APR-2018
STATISTICAL ANALYSIS PLAN(V6.0)		

MAAE/ADR, unsolicited AE/ADR and continuous solicited AE/ADR will be calculated according to the preferred terms. And the number of subjects and percentage by study vaccination number of SAE/Serious ADR (SADR), unexpected AE/ADR, MAAE/ADR, unsolicited AE/ADR and continuous solicited AE/ADR will be calculated according to the preferred terms in infants 2 to 23 months.

- ④ For subjects excluded from safety per protocol set[†], the number of subjects and the percentage of SAE/Serious ADR (SADR), unexpected AE/ADR, MAAE/ADR, unsolicited AE/ADR and continuous solicited AE/ADR will be calculated according to the preferred terms. And the number of subjects and percentage by study vaccination number of SAE/Serious ADR (SADR), unexpected AE/ADR, MAAE/ADR, unsolicited AE/ADR and continuous solicited AE/ADR will be calculated according to the preferred terms in infants 2 to 23 months.

[†] Subject excluded from safety per protocol set: Except for subjects who didn't receive study vaccination and follow-up failure.

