6.3 Additional Analyses for DDS (Data Disclosure Shell)

The following will be presented in the Safety set and Safety per Protocol set.

- Frequency and percentage by Age group (2-23 months, 2-10, 11-18, 19-64) will be presented.
- Frequency and percentage by study termination and reason not completed will be presented.
- The number of subjects of Non-SAE and the number of Non-SAE incurred shall be calculated, the incidence proportion of Non-SAE and its 95% confidence interval will be calculated using the normal approximation.
- The number of death resulting from AE shall be calculated.
- The number of subjects and percentage of Non-SAE will be calculated according to the preferred terms.

6.4 Additional Analyses for AE in the Local Product Label (Unsolicited AE Day 1-29)

The following will be presented in the Safety set and Safety per Protocol set.

- Preferred terms of Serious AE/ADR, unexpected AE/ADR will be presented respectively according to the proportion of AE in the local product label.

	CONFIDENTIAL :	Last Update Date
	THIS DOCUMENT AND INFORMATION CONTAINED HEREIN IS PROPRIETARY TO COMPANY AND IS NOT TO BE DISCLOSED WITHOUT THE WRITTEN PERMISSION OF COMPANY.	20-APR-2018
STATISTICAL ANALYSIS PLAN(V6.0)		

7. List of Table and Data Listings

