7.4 Additional Analyses for DDS (Data Disclosure Shell)

- Frequency and percentage by Age group (2-23 months, 2-10, 11-18, 19-64)
- Frequency and percentage by study termination and reason not completed
- Incidence proportion and the number of Non-SAE
- The number of death resulting from AE (frequency and percentage)
- Incidence proportion and number according to the preferred terms of Non-SAE (frequency and percentage)

7.5 Additional Analyses for AE in the Local Product Label (Unsolicited AE Day 1-29)

- Preferred terms of Serious AE/ADR, unexpected AE/ADR will be presented respectively according to the proportion.

	CONFIDENTIAL :	Last Update Date
	THIS DOCUMENT AND INFORMATION CONTAINED HEREIN IS PROPRIETARY TO COMPANY AND IS NOT TO BE DISCLOSED WITHOUT THE WRITTEN PERMISSION OF COMPANY.	20-APR-2018
STATISTICAL ANALYSIS PLAN(V6.0)		

8. Notes

- Each statistical analysis will be carried out with SAS Software version 9.4 or more recent version.
- In the descriptive statistics, mean, SD, minimum, median, and maximum will be calculated for continuous variables, and frequency and percentage for categorical variables.
- Data including sign of inequality such as “ ≥ 20 ”, “ > 20 ” will be excluded from analysis.
- All test statistics will be the results of two-sided tests with the statistical significant level of 0.05.
- The followings shall be included only in re-examination report:
 - Analysis by type of concomitant medications
 - Item ② of paragraph 6.2.3
 - Estimation of 95% confidence interval for incidence proportion of AEs by background factors
 - Paragraph 6.3, 6.4

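### Does heading the local-label output as unsolicited events to Day 29 (SAP 6.4 and 7.5) make its proportions misleading enough to change the plan?

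*SAP*

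**What the plan says.** Section 6.4 of SAP V6.0 is headed "Additional Analyses for AE in the Local Product Label (Unsolicited AE Day 1-29", and section 7.5 repeats the heading. For content, 6.4 says serious and "unexpected AE/ADR will be presented respectively according to the proportion of AE in the local product label"; the table list in 7.5 has "Preferred terms of Serious AE/ADR, unexpected AE/ADR will be presented respectively according to the proportion". The V6.0 revision table records that the regulator (MFDS) asked for this analysis, and section 8 reserves it for the re-examination report.

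The rest of V6.0 uses a shorter window. The endpoint in 4.1 is "Unsolicited AEs reported from study Day 1 (day of vaccination) through study Day 7 post-vaccination"; only medically attended events and SAEs run to Day 29. Section 2.4 has the diary report "all other AEs occurring within 7 days following immunizations, and medically attended AEs or SAEs occurring up to Day 29". Section 6.2.3 keeps the windows apart: "The frequency of unsolicited AEs (Day 1-7) and MAAE (Day 1-29) will be classified into the preferred terms".

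The protocol's diary instruction (section 3.3) agrees: "Days 8-29: record all medically attended AEs and SAEs and all medications used to treat them". Some follow-up wording is broader. If the diary is not returned, the subject or parent "will be contacted by phone to assess the occurrence of adverse events", with no restriction to attended events. Protocol 3.3 also has sites follow up mailed diaries by phone for events over the whole 28 days, and protocol 6.2.5 runs event observation to Day 29.

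**The concern.** A reader who sees only 6.4 or 7.5 could take each proportion as the share of subjects with that event at any time in 29 days. For non-serious terms the collection does not support that reading. All events are sought on Days 1-7. On Days 8-29 a non-attended, non-serious event reaches the CRF only if a follow-up contact happens to pick it up, and that may depend on how, or whether, the diary came back.

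The output concerns unexpected terms, which protocol 6.2.3 defines as those absent from the package leaflet or more specific or severe than a listed event. It is set against the local label. If proportions are understated there and nothing says so, a late-onset, non-attended reaction could look rarer than it is.

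**Working it through.** **Step 1: what the heading can mean.** Footnote 2 in protocol 6.2.3 allows any collected event not solicited on the checklist to be called unsolicited. On that reading the heading covers every recorded non-checklist event to Day 29: all unsolicited events on Days 1-7, attended events and SAEs on Days 8-29, and whatever else follow-up recorded. This is consistent with the collection rules. It differs from the 4.1 endpoint only in how long the label is applied.

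**Step 2: which rows are affected.** SAEs are sought on Days 1-29, so serious AE/ADR rows are unaffected. Only non-serious unexpected terms combine two rules.

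**Step 3: direction and size.** The planned evaluable number is 3,000 + 600 = 3,600 (SAP 2.2). Enrolment of 3,960 fits this: 3,600 × 1.10 = 3,960, and 3,960 × 0.90 = 3,564, or approximately 3,600. Days 1-7 are 7/29 = 24.1% of the window and Days 8-29 are 22/29 = 75.9%.

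For one preferred term and one 29-day window, let e be the share of affected subjects with onset on Days 1-7, and q the share of later-onset subjects who are recorded (attended, or found at follow-up). At most, the share missed is

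(1 − e) × (1 − q).

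It is a maximum because a subject with several events counts if any one is recorded. The documents give neither e nor q. Assume also a true proportion of 1%, that is 0.01 × 3,600 = 36 subjects:

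| e | q | share missed | subjects missed | shown |
|---|---|---|---|---|
| 24.1% (even onset) | 20% | 60.7% | 21.8 | 0.39% |
| 24.1% | 50% | 37.9% | 13.7 | 0.62% |
| 24.1% | 80% | 15.2% | 5.5 | 0.85% |
| 80% | 20% | 16% | 5.8 | 0.84% |
| 80% | 50% | 10% | 3.6 | 0.90% |
| 80% | 80% | 4% | 1.4 | 0.96% |
| 95% | 20% | 4% | 1.4 | 0.96% |
| 95% | 50% | 2.5% | 0.9 | 0.975% |
| 95% | 80% | 1% | 0.4 | 0.99% |

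The direction is downward in every row, but the size depends entirely on the assumed inputs. Measured against the narrower quantity that was actually collected (unsolicited Days 1-7 plus attended and serious Days 1-29), there is no shortfall.

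Nor is the figure a clean lower bound on a 29-day proportion. SAP 2.4 and 3.1 allow infants to be followed after several vaccinations, so one subject can contribute more than one 29-day window.

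**Step 4: what the SAP already supplies.** Items 1 and 2 of SAP 6.2.3 tabulate unsolicited events (Day 1-7) and attended events (Day 1-29) by expectedness, seriousness and relationship. Item 3 gives subject percentages by preferred term for serious, unexpected, attended and unsolicited AE/ADR as separate outputs. The last table shells included are those of V4.0, since superseded. They point the same way: Tables 3.1.1 to 3.1.5 give subject percentages for unsolicited events over 7 days, Tables 3.1.6 to 3.1.8 and 9.1.1 do so for attended events, and sections 8 and 10 already title their unexpected and unsolicited outputs as covering 28 days. The long-window label therefore predates 6.4.

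**Step 5: what a change would buy.** Splitting the output into Day 1-7 and attended columns would largely repeat the tables in step 4. Any pooled figure the regulator wants would stay the same. No uncollected event would be recovered, and no test, interval or threshold in 6.4 or 7.5 would move, because none is stated there.

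**The case for a change.** The best case for acting is that the fix is cheap and the readership matters. The output goes to the regulator, and it is the one place where unexpected terms are set against the label. The SAP attaches a footnote on mixed windows to its combined adverse-event analyses in 6.2 and 6.2.1, yet 6.4 has a different window in its heading and no such note. SAP 6.2.3 does not wholly fill the gap: item 2 gives frequencies rather than subject percentages, item 3 gives unexpected AE/ADR percentages without a window, and the attended and unsolicited tables by preferred term are not restricted to unexpected terms.

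The textual part of this is right: 6.4 and 7.5 do not state what enters after Day 7. That is a missing detail, however, and the rule needed to fill it appears in the objective, 2.4, the safety assessment table, 4.1, 6.2 and 6.2.3 of the same document. The V4.0 shells also show that window footnotes were placed in the tables: Table 2.1.1 has them. The V6.0 shells are not among the documents, so nobody can say that the 6.4 table lacks one.

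**Conclusion.** No change to the plan. The mismatch between heading and endpoint window is real, but the protocol's own definition permits the heading. An analyst would build the table from the non-checklist events on the CRF to Day 29 and note the collection rule beneath it, without needing an amendment.

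The remaining effect is confined to non-serious unexpected terms. Those proportions may fall below an all-events proportion over the same follow-up. On the assumed inputs above, the shortfall for a 1% term in 3,600 subjects lies between about 22 subjects and fewer than one, a range too wide to support any claim about its importance. The conclusion rests on reading unsolicited as footnote 2 allows, on the separate outputs in SAP 6.2.3 being produced as planned, and on 6.4 staying a descriptive listing with no decision rule attached.

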7.1 Distribution of Subjects

- Number of subjects contracted to the study: The number of subjects are to be collected (under contract) as contracted by the investigator.
- Number of retrieving completed CRFs: Total number of subjects whose completed CRFs.
- Number of safety assessment population: Number of safety assessment population among total number.

7.2 Baseline Characteristics

- Mean and standard deviation (SD) or frequency and percentage by gender, age, ethnic origin, weight, height, past diagnosis, pre-Immunization temperature, temperature location, pregnancy
- Frequency and percentage by vaccine site, number of previous Menveo, study vaccination number, concomitant medications.

7.3 Safety Analyses

- Incidence proportion and the number of AEs according to the baseline characteristics (frequency and percentage).
- The number of the expected serious, severity, frequency, action taken, outcome, relationship to MenACWY-CRM for Unsolicited AE (DAY 1-7) and MAAE (DAY 1-29) (frequency and percentage).
- The number of AEs for the severity, day, fever to MenACWY-CRM according to individual solicited AE (DAY 1-7) (frequency and percentage).
- Incidence proportion and number according to the preferred terms of SAE/SADR, unexpected AE/ADR, MAAE/ADR, unsolicited AE/ADR and continuous solicited AE/ADR (frequency and percentage)
- For subjects excluded from safety per protocol set[†] incidence proportion and number according to the preferred terms of SAE/SADR, unexpected AE/ADR, MAAE/ADR, unsolicited AE/ADR and continuous solicited AE/ADR (frequency and percentage).

	CONFIDENTIAL :	Last Update Date
	THIS DOCUMENT AND INFORMATION CONTAINED HEREIN IS PROPRIETARY TO COMPANY AND IS NOT TO BE DISCLOSED WITHOUT THE WRITTEN PERMISSION OF COMPANY.	20-APR-2018
STATISTICAL ANALYSIS PLAN(V6.0)		

† Subject excluded from safety per protocol set: Except for subjects who didn't receive study mediation and follow-up failure.

7.4 Additional Analyses for DDS (Data Disclosure Shell)

- Frequency and percentage by Age group (2-23 months, 2-10, 11-18, 19-64)
- Frequency and percentage by study termination and reason not completed
- Incidence proportion and the number of Non-SAE
- The number of death resulting from AE (frequency and percentage)
- Incidence proportion and number according to the preferred terms of Non-SAE (frequency and percentage)

7.5 Additional Analyses for AE in the Local Product Label (Unsolicited AE Day 1-29)

- Preferred terms of Serious AE/ADR, unexpected AE/ADR will be presented respectively according to the proportion.

	CONFIDENTIAL :	Last Update Date
	THIS DOCUMENT AND INFORMATION CONTAINED HEREIN IS PROPRIETARY TO COMPANY AND IS NOT TO BE DISCLOSED WITHOUT THE WRITTEN PERMISSION OF COMPANY.	20-APR-2018
STATISTICAL ANALYSIS PLAN(V6.0)		

8. Notes

- Each statistical analysis will be carried out with SAS Software version 9.4 or more recent version.
- In the descriptive statistics, mean, SD, minimum, median, and maximum will be calculated for continuous variables, and frequency and percentage for categorical variables.
- Data including sign of inequality such as “ ≥ 20 ”, “ > 20 ” will be excluded from analysis.
- All test statistics will be the results of two-sided tests with the statistical significant level of 0.05.
- The followings shall be included only in re-examination report:
 - Analysis by type of concomitant medications
 - Item ② of paragraph 6.2.3
 - Estimation of 95% confidence interval for incidence proportion of AEs by background factors
 - Paragraph 6.3, 6.4
